# 5.7.1.2 Bisacodyl

The bisacodyl provided by the sites to patients will be used only as directed in the CSP.

The study personnel will account for all bisacodyl dispensed to and returned from the patient. This record-keeping consists of a dispensing record that includes the identification of the person to whom the bisacodyl is dispensed, the quantity and the date of dispensing, and the amount of any unused bisacodyl returned to the investigator. This record is in addition to any drug accountability information recorded on the eCRF. Patients must return unused bisacodyl to the investigator at each visit in which new bisacodyl is dispensed, and at the final visit of the treatment period.

# **5.8 Discontinuation from study**

Patients are at any time free to discontinue from the study (IP and assessments), without prejudice to further treatment (withdrawal of consent). Such patients will always be asked about the reason(s) and the presence of any AEs. If possible, they will be seen and assessed by an investigator and Visit 4 assessments will be performed. Adverse events will be followed up (see Sections 6.3.4 and 6.3.5); and all study drugs should be returned by the patient.

Discontinued patients will not be replaced.

Patients should be discontinued in the following situations:

- Patient decision. The patient is at any time free to discontinue treatment, without prejudice to further treatment.
- Inadequate pain control after reasonable attempts to control pain have been unsuccessful
- Hepatotoxicity (significantly increased elevations in liver transaminases as defined in Section 6.3.10.2. The protocol for handling patients with elevated liver transaminases including guidelines for discontinuing patients is discussed in Section 6.3.10.2).
- Severe non-compliance to the CSP (including dosing regimen with NKTR-118 and/or prescribed opioid) as judged by the investigator in consultation with the study physician

- Incorrectly enrolled patients, involving increased safety risk. The investigator should consult with the study physician before discontinuing the patient unless there is a medical urgency.
- Patient is lost to follow-up
- The patient has a clinically significant or serious AE (eg, new or worsening heart failure) or sustained clinically significant treatment emergent abnormalities in vital signs that would not be consistent with continuation in the study, as determined by the investigator, AstraZeneca, or its representative, or the patient.
- Safety reasons as judged by the investigator
- Patient becomes pregnant
- Significantly worsened OIC refractory to medical treatment as judged by the investigator (including failure of the laxative rescue regimen)
- The patient is unable to comply with the restrictions on the use of concomitant medications as detailed in Section 5.6 (in such cases the investigator should consult with the study physician before discontinuing the patient).
- The patient is unable to tolerate the assigned dose of the study drug.

Abdominal pain has been reported as an AE in a previous trial with NKTR-118. The management of severe abdominal pain is discussed in Section 6.3.14.2.

Patients who discontinue prematurely from the study after participating in Visit 1 and receiving at least 1 dose of study drug will be asked to return to the study center for an ET visit during which assessments normally scheduled for Visit 4 (Day 85) will be obtained. This ET visit should be scheduled as soon as possible after the patient discontinues from the study. Any patient who discontinues and has clinically significant or abnormal results for any safety assessments will have an additional follow-up visit 1 week after discontinuation and at appropriate intervals thereafter, as medically indicated and determined by the investigator. AstraZeneca reserves the right to request follow-up information on any significant events on a case-by-case basis.

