### **Duration of treatment**

The study duration will be up to 14 weeks, consisting of a 12-week treatment period, and a follow-up visit 2 weeks after the last dose of study drug.

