#### 3.1.3 Final Visit (Visit 5, Week 14, Day 99)

Visit 5 will occur on Day 99 ( $\pm$ 3 days). At Visit 5, the following procedures will be performed:

- PAC-SYM will be completed.
- PAC-QOL will be completed.
- EQ-5D will be completed.
- OIC Healthcare Resource Utilization questionnaire will be completed.
- Sitting blood pressure and pulse must be measured. Please see Section 6.3.13.1 for additional details on the protocol-mandated methods for collection of vital signs. The accurate time in date, hours and minutes will be recorded for this measurement.
- Single 12-lead ECG will be obtained.
- Blood samples will be collected for laboratory assessments (clinical chemistry and hematology) and serum pregnancy test (WOCBP).
- C-SSRS to assess suicidal risk, ideation, and behavior will be completed.
- Daily maintenance and breakthrough pain opioid dosing regimens will be asked about and recorded on the appropriate eCRFs.
- Use of enema rescue medication since Visit 4 will be recorded.
- Use of concomitant medication (including bisacodyl and other laxative medication with the exception of enema) since Visit 4 will be recorded.
- AEs since Visit 4 will be recorded.

# Table 1

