#### Table 1Study plan

Date

	Enrollment	Treatment Period		Final	
Week	0	W4	W8	W12	+ 2W
Visits	1	2	3	4/ET	5
Study Day	D1	D29	D57	D85 a	D99 b
Visit Window (Days)		±3	±3	±3	±3
Concomitant medication (other than enema rescue or opioid medication) k					$\checkmark$
AEs 				$\checkmark$	$\checkmark$
Dispense study drug	$\checkmark$	$\checkmark$			
Return unused study drug				$\checkmark$	
Dispense bisacodyl	$\checkmark$	$\checkmark$			
Return unused bisacodyl				$\checkmark$	
Make appointment for next visit	$\checkmark$				

AEs Adverse events; C-SSRS Columbia Suicide Severity Scale; D Day; ECG electrocardiogram; ePRO electronic patient reported outcome; EQ-5D Euroqol 5 Dimension Instrument; ET early termination; LAR laxative adequate response; LIR laxative inadequate response; LUR laxative unknown response ; OIC opioid-induced constipation; PAC-QOL Patient Assessment of Constipation Quality of Life; PAC-SYM Patient Assessment of Constipation Symptoms; NRS Numeric Rating Scale; WOCBP women of childbearing potential

a Week 12 assessments should be performed at the time of early termination for patients who discontinue early, with the exception that patients who do not receive their first dose of study drug in Study D3820C00007 will not be required to have Week 12 assessments.

b Patients who enter the 52-week safety extension study do not need to participate in Visit 5.

c Informed consent will be collected at Visit 1 for patients who enroll directly from pivotal study D3820C00004.

d Demographics, medical and surgical history, and laxative tolerance status will be obtained from the screening visit of study D3820C00004. Complete physical examination, sitting blood pressure and pulse, PAC-SYM, PAC-QOL, EQ-5D, OIC Healthcare Resource Utilization questionnaire, triplicate ECG, urine sample collection (for urine drug screen [urine toxicology], urine pregnancy test [WOCBP], and urinalysis), blood sample collection (for laboratory assessments [clinical chemistry including total cholesterol, and hematology]), C-SSRS, and Modified Himmelsbach scale will all be obtained from Visit 8 of study D3820C00004.

e At enrollment (Visit 1) and Week 12 (Visit 4), physical examination may include optional rectal examination at the discretion of the investigator. However at Visit 4 a rectal examination is mandatory for patients who enter the safety extension study.

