### 6.3.4 Recording of adverse events

#### Time period for collection of adverse events

For patients who do not enroll in an extension study, all AEs will be collected from the time of signature of informed consent to the follow-up visit (Visit 5), whether or not related to the IP and must be recorded on the eCRF. Unsolicited reports of SAEs will also be collected for 30 days after the last dose of study drug.

For patients who enroll in an extension study, AEs and SAEs will be collected from the time of signature of informed consent to the last treatment visit (Visit 4), whether or not related to

the IP and must be recorded on the eCRF. Additional AE and SAE reporting will occur in the extension study.

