# 10. DATA MANAGEMENT BY ASTRAZENECA

### **10.1** Electronic case report form

The eCRF and the protocol are both confidential. The eCRF will be created by the CRO and programmed into the eDC system. All study sites will need internet access to access the eCRFs and will only have access to data for patients at their own study sites. Data management (DM) and other co-ordinator teams will have access to data at all study sites.

All eCRFs are to be completed by an authorized member of the investigational staff and reviewed and signed by the investigator. All entries, corrections, and alterations are to be made by the responsible investigator or an authorized member of the investigational staff. All eCRFs are to be completed in a manner that ensures accurate interpretation of data.

It is each investigator's responsibility to ensure that all discontinued orders or changes in the study or other medications entered on the patient's eCRF correspond to the entries on the patient's medical records.

The eCRFs for any patient leaving the study should be completed at the time medication is terminated for whatever reason.

The eCRFs must accurately reflect data contained in patient's records (eg, source documents).

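### For patients who stop drug early and do not enter the 52-week study, the protocol does not settle when follow-up and adverse event collection end

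*Protocol*

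**What the plan says.** All references are to the protocol.

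- **End of AE collection.** Section 6.3.4 says that, for patients who do not enroll in an extension, "all AEs will be collected from the time of signature of informed consent to the follow-up visit (Visit 5". It adds: "Unsolicited reports of SAEs will also be collected for 30 days after the last dose of study drug". For patients who do enroll in an extension, collection in this study ends at Visit 4.
- **Timing from the last dose.** The synopsis (Duration of treatment) and Section 3.1 both provide for "a follow-up visit 2 weeks after the last dose of study drug".
- **Timing by study day.** Section 3.1.3 says "Visit 5 will occur on Day 99", with a window of ±3 days. Section 3.1.2.2 also gives Day 99 for the Visit 5 appointment. Table 1 heads that column D99 but also +2W, directly after a column headed 4/ET.
- **Patients who stop early.** Sections 3.1.1 and 5.8 bring them back for an ET visit with the Visit 4 assessments. On timing, Section 5.8 says "This ET visit should be scheduled as soon as possible after the patient discontinues from the study", and a footnote to Table 1 says "Week 12 assessments should be performed at the time of early termination for patients who discontinue early". Section 5.8 then says that patients whose safety results are clinically significant or abnormal, and only they, "will have an additional follow-up visit 1 week after discontinuation", with later visits as indicated. Neither section mentions Visit 5.
- **Use of the data.** Section 11.2.1 plans a summary of AEs after the last dose, partly to look for withdrawal-type effects. Section 12.2.1 makes it one of three AE sets and takes the whole Safety population as the denominator of the proportions.

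**The concern.** The end of AE collection is tied to a visit whose date is clear for completers but not for early stoppers. A site that reads Section 5.8 alone closes such a patient at the ET visit. A site that reads Section 3.1 sees the patient two weeks after the last dose. A site that takes Section 3.1.3 literally waits until Day 99.

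Safety is the primary objective, and the post-dose AE set is meant in part to show what happens when drug is withdrawn. If the window depends on the site's reading, the proportions in that set mix patients observed for days with patients observed for months. If early stopping also differs between arms, part of any difference in post-dose AE incidence would reflect observation time. A statistical analysis plan can cut long windows back to a common length, but it cannot recover a non-serious event that nobody asked about after the ET visit.

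**Working it through.** **Inputs.** Treatment runs from Day 2 to Day 85 (Section 5.5.2). Follow-up is 14 days after the last dose (synopsis, Section 3.1) or on Day 99 ±3 (Section 3.1.3, Table 1). The delay from last dose to ET visit is not given; I assume 1 to 7 days.

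**Step 1: the plan's own figure.** Last treatment day plus two weeks: 85 + 14 = 99, which matches Day 99. If the Visit 4 morning dose is held, as Section 3.1.1 asks, the last dose is on Day 84 and 84 + 14 = 98, inside the ±3-day window. The two timings therefore agree for completers.

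**Step 2: window for an early stopper.** The post-dose window is the day of the last AE contact minus the day of the last dose.

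| Last dose | 14 days after last dose | Visit 5 on Day 99 (with ±3) |
|---|---|---|
| Day 2 | 14 days (Day 16) | 97 days (94–100) |
| Day 29 | 14 days (Day 43) | 70 days (67–73) |
| Day 57 | 14 days (Day 71) | 42 days (39–45) |
| Day 85 | 14 days (Day 99) | 14 days (11–17) |

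Two further readings depend on when the ET visit takes place:

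- *ET visit only:* 1 to 7 days under the assumed delay, or about 7 days or more if the conditional one-week visit applies.
- *Two weeks after ET* (Table 1, +2W after 4/ET): delay + 14, so 15 to 21 days under the same assumption.

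The fixed 30-day window for unsolicited serious AE reports is the same under every reading, so the spread concerns non-serious AEs.

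**Step 3: what window length does to a proportion.** The protocol gives no AE rate. As an illustration, assume a constant rate r of 0.1 to 0.4 first events per patient-month. The chance of at least one recorded post-dose AE in w days is 1 − exp(−r·w/30.4).

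| Window w | r = 0.1 | r = 0.2 | r = 0.4 |
|---|---|---|---|
| 3 days | 1.0% | 2.0% | 3.9% |
| 14 days | 4.5% | 8.8% | 16.8% |
| 70 days | 20.6% | 36.9% | 60.2% |
| 97 days | 27.3% | 47.2% | 72.1% |

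At any one rate the window alone moves the figure by a large factor. A constant rate is a crude model. Withdrawal-type symptoms would be expected to cluster soon after stopping, so the table shows sensitivity to window length and is not a forecast.

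**Step 4: the denominator.** Patients entering the 52-week study stop AE collection here at Visit 4, yet they remain in the Safety population. They can contribute little or nothing to the post-dose numerator. Fixing the timing for early stoppers therefore does not by itself make the post-dose proportion interpretable; the denominator needs attention too.

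**The case against.** The strongest reply is that this is an ambiguity with a sensible resolution. Day 99 is simply Day 85 plus 14, the nominal day for a completer. Table 1 puts +2W after 4/ET, which points to a visit two weeks after the end of treatment whenever that falls. Section 5.8, in discussing patients who withdraw, refers AE follow-up to Section 6.3.4, which runs to Visit 5. The only patients expressly excused from Visit 5 are 52-week entrants. The one-week visit is described as additional, and it gives more contact to patients with abnormal findings. The study is descriptive, with no testing.

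Much of this stands. A reader might infer that three contradictory rules are all in force. The documents do not support that: the timings coincide for completers, and the cross-references favor some Visit 5 for early stoppers. What remains is that no sentence says so, the same Table 1 column also says D99, and the two sections written for early stoppers omit the visit.

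Three other inferences are tempting:

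- *That early stoppers are the patients most likely to have post-dose events.* No figure in the protocol shows this.
- *That Section 10.1 closes AE collection*, because it says "The eCRFs for any patient leaving the study should be completed at the time medication is terminated for whatever reason". That sentence concerns completing forms and does not set the end of AE collection. Nor does the Section 6.3.4 paragraph on unresolved AEs, which does not say when the last assessment takes place.
- *That post-dose incidence will be biased between arms.* That needs stopping to differ by arm. In Phase II (Section 1.4), the 12 discontinuations for AEs were 10, 1 and 1 at 50, 25 and 5 mg. Most were at a dose not used here, so this makes the mechanism plausible without giving its size.

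**Conclusion.** The point holds as an unreconciled set of follow-up rules for one group: dosed patients who stop early and do not enter the 52-week study. For them the window for non-serious post-dose AEs is a few days (assumed 1 to 7), 14 days, or up to about 97 days, according to which section the site follows. The 97 days is the extreme case, with the last dose on Day 2 and Day 99 taken literally. Completers are not affected, and the 30-day window for unsolicited serious AE reports is fixed.

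The effect on the planned post-dose AE summary cannot be sized from the protocol, which gives neither an early stopping rate for this study nor an AE rate. The percentages in the working rest on assumed constant rates. The point should still be settled in the protocol, because it decides which events are collected and the loss under the shortest reading cannot be repaired at analysis.

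**What to change.** Reconcile Sections 3.1.1, 3.1.3, 5.8 and 6.3.4 and Table 1 so that one follow-up rule covers every dosed patient not entering the 52-week study, including early stoppers who have not withdrawn consent. The sponsor must choose the rule. The timing from last dose already in the synopsis and Section 3.1 would give the same 14-day nominal window whatever the day of stopping. State that AE collection ends at that visit and that the one-week visit in Section 5.8 is additional to it.

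In Section 12.2.1, tabulate AEs after the last dose over that window, with a denominator of patients who have post-dose follow-up in this study, since collection for 52-week entrants ends at Visit 4.

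The cost is amendment wording and at most one follow-up visit per early stopper, a visit the synopsis already provides for. Patients who withdraw consent will still have shorter windows, and no wording can prevent that.

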# 6. COLLECTION OF STUDY VARIABLES

### 6.1 Recording of data

The electronic Data Capture (eDC) system will be used for data collection and query handling. The investigator will ensure that data are recorded on the eCRFs as specified in the CSP and in accordance with the instructions provided.

The investigator ensures the accuracy, completeness, and timeliness of the data recorded and of the provision of answers to data queries according to the Clinical Study Agreement (CSA). The investigator will sign the completed eCRFs. A copy of the completed eCRFs will be archived at the study site.

# 6.2 Data collection and enrollment

### 6.2.1 Screening and demographic measurements

The following data will be collected and recorded on the appropriate sections of the eCRF at the time of the enrollment visit (Visit 1) (refer to the Study Plan, Table 1). Some of these measures will have been obtained in the original pivotal study (D3820C00004) that patients participated in as indicated below:

- Signed informed consent forms (ICFs) will be obtained.
- Demography (date of birth, sex, and race) (obtained from Visit 1 of previous study D3820C00004)
- Review of I/E criteria
- Medical and surgical history (including OIC history) (obtained from Visit 1 of previous study D3820C00004). Any ongoing AEs at the end of the previous study, as well as resolved AEs meeting medical history criteria, should also be entered as medical history in this study.
- Complete physical examination (including height, weight) (obtained from Visit 8 of previous study D3820C00004). May include optional rectal examination at discretion of investigator.
- Vital signs (sitting blood pressure and pulse, body temperature, respiratory rate) (obtained from Visit 8 of previous study D3820C00004)
- LIR, LAR, LUR status (obtained from Visit 1 of previous study D3820C00004)
- PAC-SYM (obtained from Visit 8 of previous study D3820C00004)
- PAC-QOL (obtained from Visit 8 of previous study D3820C00004)
- EQ-5D (obtained from Visit 8 of previous study D3820C00004)
- Pain level (NRS) average over the previous 7 days
- OIC Healthcare Resource Utilization questionnaire (obtained from Visit 8 of previous study D3820C00004)
- Triplicate 12-lead ECG (obtained from Visit 8 of previous study D3820C00004)

- Laboratory assessments (obtained from Visit 8 of previous study D3820C00004)
- Urine drug screen (obtained from Visit 8 of previous study D3820C00004)
- Urine pregnancy test (WOCBP) (obtained from Visit 8 of previous study D3820C00004)
- U/A (obtained from Visit 8 of previous study D3820C00004)
- C-SSRS (obtained from Visit 8 of previous study D3820C00004)
- Modified Himmelsbach scale (obtained from Visit 8 of previous study D3820C00004)
- Concomitant medications ongoing at the end of the previous study D3820C00004
- Daily maintenance opioid dosing regimen and opioid medication for breakthrough pain

#### 6.2.2 Additional procedures including follow-up procedures

Additional procedures (and follow-up procedures) during the visits after enrollment are referenced in the Study Plan (Table 1).

### 6.3 Safety

The PI is responsible for ensuring that all staff involved in the study is familiar with the content of this section.

#### 6.3.1 Safety variables

Safety variables include:

- Incidence, nature, and intensity of AEs, treatment-related AEs, SAEs, AEs leading to discontinuation, and specific safety areas of interest.
- Mean daily opioid dose for Weeks 4 and 12.
- Mean bisacodyl dose per week for Weeks 4 and 12.
- Change from baseline in the mean NRS pain score for Weeks 4, 8, and 12.
- Observed values and change from baseline in composite score in modified Himmelsbach scale for the evaluation of centrally mediated opioid withdrawal symptoms at Week 12.
- Changes in vital signs and physical examination.

- Changes in laboratory assessments (ie, chemistry, hematology, and U/A).
- Changes in ECGs.

#### 6.3.2 Definition of adverse events

An AE is the development of an undesirable medical condition or the deterioration/exacerbation of a pre-existing medical condition following or during exposure to a pharmaceutical product, whether or not considered causally related to the product. An undesirable medical condition can be symptoms (eg, nausea, chest pain), signs (eg, tachycardia, enlarged liver), or the abnormal results of an investigation (eg, laboratory findings, ECG). In clinical studies, an AE can include an undesirable medical condition occurring at any time, including run-in or washout periods, even if no study treatment has been administered.

The term AE is used to include both serious and non-serious AEs.

#### 6.3.3 Definitions of serious adverse event

An SAE is an AE occurring during any study phase (ie, run-in, treatment, washout, follow-up), that fulfills 1 or more of the following criteria:

- Results in death
- Is immediately life-threatening
- Requires in-patient hospitalization or prolongation of existing hospitalization
- Results in persistent or significant disability/incapacity or substantial disruption of the ability to conduct normal life functions
- Is a congenital abnormality or birth defect
- Is an important medical event that may jeopardize the patient or may require medical intervention to prevent 1 of the outcomes listed above

For further guidance on the definition of an SAE, see Appendix B to the CSP.

